10.4 STATISTICAL ANALYSES

10.4.1 General Approach

Missing Data

Subjects who discontinue early or are lost to follow-up will be censored from applicable analyses at the last date where the study outcome can reliably be determined (e.g., date of last available TBS specimen without parasitemia).

It is anticipated that some event dates required for safety analyses may be incomplete. If the event onset day is unknown, then the date will be imputed as the last date the subject could reliably be assumed to be event free (e.g., the previous study visit where the event was not reported). If the resolution day is incomplete, then the date will be imputed as the date that the event was reliably known to no longer be present.

It is anticipated that some TBS results will be missing. In those instances where one TBS is missed, the result will be imputed to be the same as the result of the next TBS. Up to three such single missing TBS will be allowed in a research subject during the 26 weeks of follow-up without disqualifying the participant from the ATP population (as long as the individual meets other requirements for ATP, such as receiving all three immunizations within the correct time windows). If there are situations where two or more consecutive TBS are missed, the result will again be imputed to be the same as the result of the next TBS, and the research subject will be included in the m-ITT population (as long as the individual meets other requirements for m-ITT, such as receiving all three immunizations). If the only TBS missed is the last, there will be no imputation, the missing data point will be ignored, and the individual may be included in the ATP population. If the two or more TBS missed are the last, there will be no imputation, the missing data points will be ignored, and the individual may be included in the m-ITT population. However, if more than the last two TBS are missed, the individual will not be included in proportional efficacy analyses, although may be included in time-to-event efficacy analyses.

Multiple Testing

The primary VE endpoint is the VE against *Pf malaria with symptoms*. The overall vaccine efficacy will be assessed over all participants.

No multiplicity adjustment will be made for secondary efficacy or safety endpoints.

10.4.2 Safety Analyses

The primary safety endpoint is the occurrence of an SAE between V1 and 26 weeks after V3 which is at least possibly related to treatment. Serious AEs which meet this definition will be summarized in frequency tables and listings according to system organ class, preferred term, relatedness, and severity. The primary safety analysis will be performed using the ITT population and according to treatment received at V1, regardless of any randomization or allocation errors. All SAEs will be coded using the Medical Dictionary for Regulatory Activities (MedDRA) and summarized using frequencies, proportions, and exact 95% CIs for proportions. Rates of SAEs (overall and for any system organ class or preferred term with at least 5 events in either group) will be compared using two-sided 0.05 level Fisher's Exact Tests.

Secondary safety endpoints include the occurrence of unsolicited AEs, laboratory abnormalities, and solicited AEs in the ITT population. Unsolicited AEs documented from V1 to 14 days following V3 will be coded using MedDRA and summarized in frequency tables according to system organ class, preferred term, relatedness, and severity. Summaries will be provided overall and according to the vaccination number (1, 2, or 3) immediately prior to AE onset. Rates of unsolicited AEs (overall and for any system organ class or preferred term with at least 5 events in either group) will be compared using two-sided 0.05 level Fisher's Exact Tests. Adverse events leading to premature discontinuation from the study will be listed separately. Clinically relevant laboratory abnormalities recorded in the 14 days after V3 will be summarized in frequency tables by type, grade, and clinical relevance.

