- Five percent or more of the vaccinees enrolled at any time point in one arm (calculated as 5% of the vaccinees in the full study roster enrolled to date, as long as there are at least three subjects with the AE) experience the same severe (grade 3) AE during the periods of AE collection deemed possibly, probably or definitely related to study product administration (PfSPZ Vaccine or NS), or experience the same grade 3 laboratory abnormality on day V2 + 14 or day V3+14. Grade 3 AEs deemed possibly, probably or definitely related to malaria (as opposed to PfSPZ Vaccine or to NS) will not count toward meeting this criterion. The site, where clinical staff are blinded, can only monitor total populations (vaccine plus placebo recipients) and if a 5% threshold is reached, unblinded study staff (e.g., the head of Pharmaceutical Operations) will need to confirm that the total indeed constitutes 5% of vaccinees. Note that we have considered using Grade 2 rather than Grade 3 laboratory abnormalities, but drops in hemoglobin, neutrophils, platelets and sometimes other blood count indices meeting Grade 2 criteria for severity are common in African pediatric populations.
- One participant experiences an SAE deemed possibly, probably or definitely related to study product. This criterion will not be met if it turns out that the participant received NS. SAEs related to malaria or to antimalarial treatment which are expected, will be reported expeditiously but will not fulfill this criterion. If the SAE is unexpected with respect to malaria or antimalarial treatment, it will fulfill the criterion.

If either of these criteria appear to be met by ongoing surveillance at the site, the principal investigator will engage the head of Pharmaceutical Operations on site, or his/her designee, to

follow unblinding procedures (see **Section 6.3.3** for a description). To meet the criteria, the subjects must actually have received PfSPZ Vaccine and not NS placebo.

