9.11.2 Definition of Serious Adverse Events (SAE)

An adverse event (AE) or suspected adverse reaction is considered "serious" if, in the view of either the investigator or sponsor, it results in any of the following outcomes:

- death,
- a life-threatening adverse event,
- inpatient hospitalization or prolongation of existing hospitalization,
- a persistent or significant incapacity or substantial disruption of the ability to conduct normal life functions, or

Important medical events that may not result in death, be life-threatening, or require hospitalization may be considered serious when, based upon appropriate medical judgment, they may jeopardize the participant and may require medical or surgical intervention to prevent one of

the outcomes listed in this definition. Examples of such medical events include allergic bronchospasm requiring intensive treatment in an emergency room or at home, blood dyscrasias or convulsions that do not result in inpatient hospitalization.

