9.11.4 Time Period and Frequency for Event Assessment and Follow-Up

The occurrence of an adverse event (AE) or serious adverse event (SAE) may come to the attention of study personnel during study visits and interviews of a study participant presenting for medical care, or upon review by a study monitor.

All AEs including local and systemic reactions not meeting the criteria for SAEs will be captured on the appropriate case report form (CRF). Information to be collected includes event description, time of onset, clinician's assessment of severity, relationship to study product (assessed only by those with the training and authority to make a diagnosis), and time of resolution/stabilization of the event. All AEs occurring while on study must be documented appropriately regardless of relationship. All AEs will be followed to adequate resolution.

Any medical condition that is present at the time that the participant is screened will be considered as baseline and not reported as an AE. However, if the study participant's condition deteriorates at any time during the study after enrollment, it will be recorded as an AE.

Changes in the severity of an AE will be documented to allow an assessment of the duration of the event at each level of severity to be performed. AEs characterized as intermittent require documentation of onset and duration of each episode.

At each study visit, the investigator will inquire about the occurrence of AE/SAEs since the last visit. Events will be followed for outcome information until resolution or stabilization.

If a diagnosis is clinically evident (or subsequently determined), the diagnosis rather than the individual signs and symptoms or lab abnormalities will be recorded as the AE.

All solicited (see **Table 12** below) and unsolicited AEs will be recorded through Day 7 after each injection. Injection site reactions will be assessed until Day 7 after injection (PfSPZ Vaccine or normal saline) or until resolved.

After the periods specified above only unsolicited aEs, SAEs, UPs, and new onset of chronic illness (NOCI) will be recorded.

Table 12. Solicited Adverse Events

Laboratory adverse events¹	
Hemoglobin (decreased hemoglobin)	Platelet count (thrombocytopenia or thrombocytosis)
WBC (leukopenia or leukocytosis)	Creatinine (Cr) (increased Cr)
ANC (neutrophil count decreased) or AGC (granulocyte count decreased)	ALT (increased ALT)

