10.1 STATISTICAL HYPOTHESIS

Primary Endpoints

Safety: The primary safety endpoint is the proportion of vaccinees experiencing related SAEs from V1 to 26 weeks after V3. There is no formal hypothesis test associated with this primary safety endpoint. Rather, the proportion of subjects experiencing related SAEs will be presented for each arm separately using frequencies, percentages, and descriptive 95% confidence intervals (CIs).

Efficacy: the primary efficacy endpoint is the vaccine efficacy against *malaria with symptoms*. For this protocol, there is a primary and a secondary case definition of *Pf malaria with symptoms*.

The primary case definition is as follows:

Pf malaria with symptoms is defined as a positive thick blood smear at a density of >1000 P/uL plus:

- Measured axillary temperature ≥ 37.5 degrees Celsius or history of fever (subjective or objective) in the last 24 hours, or,
- Symptoms of malaria –
 - Verbal individual (individual able and willing to answer questions): A verbal individual is considered symptomatic if reporting at the time of evaluation at least two of the following symptoms/symptom groups: headache, chills and/or rigors, malaise and/or fatigue, dizziness and/or light-headedness, myalgias and/or arthralgias; or
 - Non-verbal individual (small child or any individual unable or unwilling to answer questions): A non-verbal individual is considered symptomatic if manifesting at the time of evaluation at least two of the following signs/sign groups: drowsiness, irritability and/or fussiness, inability and/or refusal to eat or drink, prostration; or
- Any individual: Signs of severe malaria (e.g. impairment of consciousness, severe anemia, hemoglobinuria, acute kidney injury, etc.).

The secondary case definition is as follows:

Pf malaria with symptoms is defined as a positive thick blood smear at a density of > 0 P/uL plus:

- Measured axillary temperature ≥ 37.5 degrees Celsius or history of fever (subjective or objective) in the last 24 hours, or,
- Symptoms of malaria as defined in the primary case definition; or
- Meeting criteria for severe malaria

The formal hypothesis associated with the primary efficacy endpoint is a superiority test of

$$H_0: VE = 0 \text{ versus } H_A: VE < > 0$$

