10.4.3 Efficacy Analysis

9.4.3.1 Primary: VE against Pf *malaria with symptoms*

The primary efficacy analysis will be the modified Intention to Treat (mITT).

The primary efficacy analysis will be based on time to the first Pf *malaria with symptoms*. Entry into the risk set begins on the latter of a) 14 days after completing the primary vaccination series (V3 + 14 days) or b) 28 days after initiating treatment for a parasitemia event that was detected on or before V3 + 14 days, whichever comes later. Time-to-event is defined as the number of days between entry into the risk set and date of first Pf *malaria with symptoms*; subjects who do not experience the event by 26 weeks after V3 will be censored from the primary analysis or earlier date of last negative TBS result.

The survival patterns will be described by Kaplan-Meier curves for each arm and compared by the logrank test between two arms. The protective efficacy will be assessed from the Cox proportional hazards model with treatment arm as the regressor, and the vaccine efficacy will be estimated as one minus the hazard ratio.

As a secondary efficacy analysis, the cumulative probability of Pf *malaria with symptoms* through 26 weeks post V3 will be presented for each treatment arm and compared across arms based on Kaplan-Meier estimates along with 95% confidence intervals. This estimation accounts for right censoring and the comparison should be equivalent to Fisher's exact test in case of no censoring.

Sensitivity analyses will include an ITT and ATP analysis with entry into the risk set as with the mITT analysis, and ATP analyses with entries into the risk set at time of first vaccination and at V3.

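### The overall SAE comparison counts malaria admissions with all other serious events, and no pooled comparison of the other events is planned

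*Protocol*

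**What the plan says.** - **The test.** Protocol 10.4.2, repeated in SAP 3.1: "Rates of SAEs (overall and for any system organ class or preferred term with at least 5 events in either group) will be compared" by Fisher's exact test at the two-sided 0.05 level. Neither section sets malaria aside.
- **The endpoint.** The same paragraph opens with "The primary safety endpoint is the occurrence of an SAE between V1 and 26 weeks after V3 which is at least possibly related to treatment". Section 10.1 says of that endpoint: "There is no formal hypothesis test associated with this primary safety endpoint".
- **What is recorded.** Section 9.11.4: "All AEs occurring while on study must be documented appropriately regardless of relationship". The diagnosis, where known, is the AE term. Section 9.11.2 makes an event serious on "inpatient hospitalization or prolongation of existing hospitalization", among other outcomes. Malaria is not exempted.
- **The efficacy side.** Malaria with symptoms leading to hospitalization is an exploratory efficacy endpoint (synopsis and section 4).
- **The pausing rule.** In the subsection headed 7.1.1 within section 8.1: "SAEs related to malaria or to antimalarial treatment which are expected, will be reported expeditiously but will not fulfill this criterion". Grade 3 AEs attributed to malaria are also left out of the pausing count.
- **Unsolicited AEs.** Section 10.4.2: "Unsolicited AEs documented from V1 to 14 days following V3 will be coded using MedDRA and summarized in frequency tables".

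**The concern.** A malaria admission is recorded as an SAE, and the SAE window covers the transmission season. The trial is planned around a difference in malaria between arms: section 10.2 takes a control rate of at least 0.35 and vaccine efficacy of 0.5. So the overall SAE comparison measures any harm minus the malaria prevented. The bias has a known direction: the better the vaccine works, the safer it looks on this line, and a larger trial would not remove it.

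The comparisons by system organ class and preferred term separate malaria only in part. They test single classes and terms with at least 5 events. An excess spread thinly over several of them is tested only in the overall line, where prevented malaria offsets it. A report of no difference in SAEs, or of fewer SAEs, could then partly restate efficacy.

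**Working it through.** **1. The plan's own safety figures.** Section 10.2 gives within-arm detection for n = 120. They reproduce: (1 − 0.0008)^120 = 0.908, 1 − (1 − 0.019)^120 = 0.900, and 0.99^120 = 0.299 (Table 13). The plan gives no power for a between-arm SAE comparison and no SAE or serious-malaria rate.

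**2. Which SAEs does the Fisher sentence cover?** The paragraph in 10.4.2 first defines related SAEs, then says all SAEs will be coded and summarized, then gives the test. Section 10.1 says the related-SAE endpoint carries no formal test. The reading consistent with 10.1 is therefore that the test is on all SAEs. If related SAEs were meant, 10.4.2 would contradict 10.1. The text needs clarifying either way.

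**3. Inputs for the overall comparison.**
- From the documents: about 134 per arm, two-sided 0.05 Fisher test, efficacy 0.5 (section 10.2, for malaria with symptoms).
- Assumed: non-malaria SAE risk 1% in controls and 6% in vaccinees; control malaria-SAE risk m from 0.35% to 8%; the same 50% efficacy against malaria SAEs; independent risks.

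**4. Formulas.**
- Any SAE, controls: 1 − 0.99(1 − m).
- Any SAE, vaccinees: 1 − 0.94(1 − m/2).
- Difference: 0.99(1 − m) − 0.94(1 − m/2) = 0.05 − 0.52m, which reaches zero at m = 0.05/0.52 = 9.6%.
- Power: exact, by enumerating both binomial counts.
- Serious share of control malaria cases implied by m: m/0.35.

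| m | Implied serious share | Any SAE, control | Any SAE, vaccine | Ratio | Power |
|---|---|---|---|---|---|
| 0 (malaria removed) | – | 1.0% | 6.0% | 6.0 | 49.0% |
| 0.35% | 1% | 1.3% | 6.2% | 4.6 | 42.2% |
| 1% | 3% | 2.0% | 6.5% | 3.3 | 32.0% |
| 2% | 6% | 3.0% | 6.9% | 2.3 | 21.5% |
| 4% | 11% | 5.0% | 7.9% | 1.6 | 10.3% |
| 8% | 23% | 8.9% | 9.8% | 1.1 | 3.4% |

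Part of this loss is plain noise from adding common events to both arms. With zero efficacy in the same model (vaccinee risk 1 − 0.94(1 − m)), power is 45%, 38%, 31%, 24% and 17% for the five non-zero values of m. The rest of the fall is the offset from prevented malaria.

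**5. The 5-event floor.** With 134 per arm, 5 v 0 gives p = 0.060 and 6 v 0 gives p = 0.030, so the floor costs almost nothing for a single term. The gap is for scattered events. For instance, 8 v 1 non-malaria SAEs gives p = 0.036 when pooled, but if no class or term among them reaches 5, none is tested on its own.

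**6. Unsolicited AEs.** The window runs from day 1 to day 43, 42 days. Table 10 gives dry-season incidence of 0.07 (2018) and 0.16 (2019) at ages 4–10. Read as per half-year season and with no credit for AL, expected control cases are 134 × [1 − exp(−0.07 × 42/182.5)] = 2.1 and, with 0.16, 4.8. Efficacy of 50% would remove 1.1 to 2.4. If the whole window fell in the wet season (0.77 to 0.86), the figures would be about 22 to 24 cases and 10 to 11 removed.

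**The case against.** **The primary endpoint is protected.** It counts only related SAEs, and section 9.11.3 classes an event definitely due to another etiology as Not Related. A smear-confirmed malaria admission should fall outside it. This stands: a reader might infer that the primary safety result is distorted, and the documents do not support that.

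**Unsolicited AEs hardly overlap with malaria follow-up.** Their window ends where the efficacy risk set begins. It follows AL clearance, and section 5.2.3 places vaccination in the dry season with transmission close to nil. This also stands, so the point should not be extended to unsolicited AEs on equal terms. Some overlap remains possible: vaccination may run to July, when the wet season starts, and section 5.1 leaves the second AL course open while 5.2.3 says it will not be given.

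**Malaria is already visible.** Class and term tables show it, and hospitalized malaria by arm is an exploratory endpoint. True, but none of these tests the remaining SAEs together.

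**The losses depend on assumed rates.** Admissions may be rare in 6-to-10-year-olds contacted at least every two weeks, treated promptly and with doctors always available. At m = 0.35% the loss is 49.0% to 42.2%. Even with malaria removed, power is only 49.0% for a sixfold excess, so sample size is the first limit. Both points stand.

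**All-cause SAEs are a legitimate net measure.** The risk section names breakthrough infection from inadequate attenuation as a theoretical vaccine risk, and a comparison without malaria would leave it out. This is a good reason not to replace the all-cause comparison.

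**Conclusion.** The point holds for the overall SAE comparison, on the all-cause reading that fits section 10.1. That comparison mixes an efficacy outcome into a safety result, with a bias toward apparent safety, and no pooled comparison of the other SAEs is planned. The pausing rule already makes the distinction for expected malaria SAEs.

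The size cannot be fixed from the documents. In the assumed 6% v 1% case the ratio falls from 6.0 to between 4.6 and 1.1 over the range shown. If malaria SAEs are near zero, the two analyses coincide. These figures rest on 50% efficacy against serious malaria, independent risks and invented SAE rates.

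A reader might infer that the plan will hide a real safety signal. The documents do not support that: it would take both an excess of scattered non-malaria SAEs and a material malaria-SAE rate, and neither is given. If the sentence means related SAEs only, the concern largely falls away, leaving the conflict with 10.1. This is a low-cost improvement to a supporting analysis.

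**What to change.** In Protocol 10.4.2 and SAP 3.1:

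1. State whether the Fisher comparison is on all SAEs or related SAEs, and align this with section 10.1.
2. Keep the all-cause comparison. Add beside it a between-arm comparison of SAEs other than malaria and its complications, using a MedDRA term list and a blinded attribution rule fixed before unblinding.
3. Show malaria SAEs by arm in their own row, so that a breakthrough infection stays visible.
4. For unsolicited AEs, add one sensitivity row without malaria.

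The cost is a few lines of text and a few table rows, with no new data. The real work is the blinded rule for deciding which complications belong to malaria. Because that rule involves judgement, the all-cause comparison should stay alongside.

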10.4.3 Efficacy Analysis

9.4.3.1 Primary: VE against Pf *malaria with symptoms*

The primary efficacy analysis will be the modified Intention to Treat (mITT).

The primary efficacy analysis will be based on time to the first Pf *malaria with symptoms*. Entry into the risk set begins on the latter of a) 14 days after completing the primary vaccination series (V3 + 14 days) or b) 28 days after initiating treatment for a parasitemia event that was detected on or before V3 + 14 days, whichever comes later. Time-to-event is defined as the number of days between entry into the risk set and date of first Pf *malaria with symptoms*; subjects who do not experience the event by 26 weeks after V3 will be censored from the primary analysis or earlier date of last negative TBS result.

The survival patterns will be described by Kaplan-Meier curves for each arm and compared by the logrank test between two arms. The protective efficacy will be assessed from the Cox proportional hazards model with treatment arm as the regressor, and the vaccine efficacy will be estimated as one minus the hazard ratio.

As a secondary efficacy analysis, the cumulative probability of Pf *malaria with symptoms* through 26 weeks post V3 will be presented for each treatment arm and compared across arms based on Kaplan-Meier estimates along with 95% confidence intervals. This estimation accounts for right censoring and the comparison should be equivalent to Fisher's exact test in case of no censoring.

Sensitivity analyses will include an ITT and ATP analysis with entry into the risk set as with the mITT analysis, and ATP analyses with entries into the risk set at time of first vaccination and at V3.

